The randomized clinical trial of adding weekly PRO

Design and setting

The main part of the study consists of a multicenter randomized trial in order to assess the effects of the weekly PRO intervention. The design follows the overall setup presented in the publication by Denis et al, however, adapted to a Danish setting, as described above, including the Danish guidelines for evaluating CT scan in both arms². The randomization and baseline data collection will be made in the IT system (AmbuFlex) by the oncologist at the time of enrollment.

Implementation of the intervention

The intervention is illustrated in Figure 1. *In the experimental arm*, patients will be asked to fill in the PRO questionnaire every week via an internet connection, and they will also be asked to fill in HRQoL questionnaires at any outpatient attendance. However, if their weekly reported symptoms result in a notification, the clinician will contact the patient, and after verification of symptoms, schedule a visit at the clinic for physical examination and evaluation. If relapse or progression of disease is suspected an extra CT scan will be made, otherwise the patient will continue response evaluation/follow-up according to the usual schedule. The clinicians are allowed to reschedule the CT scan based on the phone call alone.

Both the HRQoL measurements and the web application will be administered through a web page that is designed for use on mobile phones, tablets and laptops(AmbuFlex¹⁹). The data will automatically be transferred in real time to a computer server, where notifications are generated and sent to clinicians if the prespecified symptom thresholds are exceeded. Data is automatically scored and will be available in easily interpretable visual reports in the AmbuFlex system.

If participants do not fill in the web-based questionnaire at pre-specified times, a reminder will be sent using a text message to their mobile phone and a message will appear for the clinical staff at the daily notification list.

[figure not shown]

Figure 1. Flow-chart showing the PRO-intervention in the randomized clinical trial.

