- Categorization of the performed CT scan as prescheduled as a result of a PRO notification

Study period:

Patients will be followed for two years after inclusion in case of non-progressive disease. In case of progressive disease or relapse, the patient will exit the study. For survival analysis and further evaluation, patients will be followed until death or up to 5 years from inclusion.

Endpoints:

The primary outcome measures that will be compared between the experimental and control arm is overall survival with an observation time of 24 months.

The secondary outcome measures are

- Performance status at the time of progressive disease
- Progression-free survival
- Health-related quality of life
- Cost-effectiveness and hospital resource use and costs
- Type of treatment at the time of progressive disease

Time to progression as well as performance status at progression compared to performance status at enrolment into the study may be used to investigate, whether the intervention leads to earlier detection of and better performance status at the time of progression. Quality of life differences may provide insights on possible other patient perceived benefits to the web-mediated follow-up.

Sub-studies

A parallel research project has been financed and will focus on benefit in terms of quality of life and better patient involvement through qualitative interviews with patients included in the study. With qualitative interviews, we aim to describe how participants experience the web-based PRO application and to explore the mechanisms of action related to PROs as a mean of patient involvement. Moreover, we aim at exploring how the intervention influences patients' fear of cancer recurrence and their psychosocial well-being. We will apply the method of an interpretive description as an inductive, flexible research strategy to generate knowledge relevant within a clinical context²². Individual semi-structured interviews will be conducted with 8-10 patients from each arm. After one year, follow-up interviews will be conducted with the same participants in order to explore transformations in the patients' experiences and give new insights in barriers and opportunities for patient involvement in follow up of lung cancer (For details, see appendix, sub-study 1).

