Generalizability of any study finding is important when considering future implementation processes. Previous trials of behavioural interventions among cancer patients have found that patients who choose not to participate have lower education and income, are more often single and have lower survival compared to participants²³⁻²⁵. In another parallel study, we will use registry data and baseline health-related quality of life to compare differences between participants versus non-participant. The aim is to assess differences in their lung cancer disease, symptom- and comorbidity burden, and socioeconomic characteristic. By understanding these differences, we hope to be able to improve future planning of PRO use in lung cancer follow-up for all patients (See appendix for details, sub-study 2).

Intervention costs, and the derived hospital resource use and costs (number of contacts, visits, scans etc.) can be used to estimate the difference in costs in the two arms. Data will be collected retrospectively upon completion of the trial (see Appendix, sub-study 3). Together with information on effects regarding the other endpoints (including health-related quality of life), this can provide a basis for a health economic evaluation of the intervention.

Data collection and analysis

Baseline information on age, gender, Charlson's comorbidity index (extracted from central registry), histology (extracted from the pathology database), TNM stage and treatment type will be noted. During the study period, the number of CT scans will be recorded, as well as disease status and deaths including the cause of death. After verification of progressive disease, the following cancer treatment modalities will be registered. Data will be filed in and stored electronically using the AmbuFlex system and transferred to REDCap (Research Electronic Data Capture) for further data management.

Data on resource use and costs for the health economic evaluation will be collected as a retrospective study upon completion of the trial, using 1) expert assessment for time and material spent on the intervention and 2) individual patient cost data

extracted from the National Patient Registry linked to the National Cost Database (See appendix).

Power calculation

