The project is based in the Regional Hospital in Herning, but the intention is a wide collaboration across hospitals to recruit as many participants as quickly as possible which is also reflected in the broad collaboration of the project group (see organization below).

Implementation of PRO data for clinical practice is complex, both in terms of organization and technology. PRO data system AmbuFlex has already been incorporated in every day clinical practice in the oncology department in Herning, based in the Central Region of Denmark, and is already available in many oncology departments in Denmark, facilitating rapid recruitment and increasing the possibility of successful completion of the project¹⁹.

PRO data collection in oncology departments, where PRO data is not incorporated in everyday practice, will be implemented by using the experience gathered by the collaboration between WestChronic /AmbuFlex and the Danish Cancer Society, where PRO data were collected from lung cancer patients from seven hospitals from different regions in Denmark in 2013-2015²⁹. This project also demonstrated large differences between hospitals, which could be due to differences in regional health-it resources. To ensure fast and reliable implementation, the project will be started stepwise in phases in regions with actual access to AmbuFlex. The pilot phase will be conducted in the oncology department of the Regional Hospital in Herning. The first phase will be started in oncology departments of Central Denmark Region (in Herning and Aarhus), the second phase includes the North Denmark Region (in Aalborg). The third phase will include Region Zealand, and if technically possible, other regions.

Publications

The study will be published after completion, when the final analyses have been performed, in international peer-reviewed journals. The protocol committee writes the first draft and the Vancouver declaration will be followed in all publications based on this study. The names on the author list will be given according to the active participation in the design of the protocol, in the recruitment of patients.

Project organization

The project is intended for a PhD thesis.

Following are members of the protocol committee:

[name] [name], PhD student, West Jutland Hospital, Herning
[name], DMsc., Senior Consultant, West Jutland Hospital, Herning

[name] [name], PhD, Senior Consultant, Professor, University Hospital Aarhus and West Jutland Hospital, Herning

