Appendix, sub-study 3:

Health economic evaluation alongside the ProWide clinical trial

This document describes the data collection, outcome measures, and analysis for a health economic evaluation of the weekly internet-based detection of progressive disease in lung cancer.

The health economic evaluation will be conducted after the completion of the ProWide trial. The evaluation will use the trial efficacy data supplemented by a cost assessment based on data collected outside the trial and be conducted in accordance with the recommended practice for health economic evaluation (1).

Aims

The study will assess the incremental cost per quality-adjusted life year gained (QALY) for patients with lung cancer (corresponding to the inclusion criteria) of using a weekly internet-based tool for systematic self-reporting of symptoms compared with standard care, that is, not-systematic reporting of symptoms of progressive disease.

The assessment will take a 1-year perspective and a 5-year perspective

Study perspective:

The evaluation will use a hospital perspective only

Data

Data for the assessment of patient unit costs (intervention costs; derived hospital costs) will be collected outside the trial:

Intervention costs will be assessed using structured interviews with study nurses, doctors and other relevant personnel at 3-4 of the participating hospitals. The purpose of these interviews is to describe and quantify the resource use relating to the intervention (e.g. the number of telephone calls, clinical staff time spent on patient contacts, IT support etc.) and relating to patient telephone contact in the control arm. The resource used will be valued using average net salary information for the relevant

type of personnel plus social costs in accordance with the recommendations for cost assessment in health care.

Derived hospital costs will be assessed in a research project based at the National Board of Health Data (Sundhedsdatastyrelsen) or Statistics Denmark. Data on resource use – eg. Procedures, admissions and dates, ambulatory contacts, and hospital costs for each of the participating patients will be collected from the National Patient Registry and linked with patient data from the National Cost Database. The research project is subject to approval from the Danish Data Protection Agency.

Mortality data are collected in the trial and survival analysis for the accumulation of life years will be undertaken as part of the statistical analysis plan.

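### The number of calls behind the intervention cost is to come from retrospective staff interviews at 3-4 hospitals, although the trial's own system generates notifications patient by patient at every site

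*Combined protocol and SAP*

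**What the plan says.** The Endpoints section lists "Cost-effectiveness and hospital resource use and costs" among the secondary outcomes. Appendix sub-study 3 (Data) splits cost into two components and says that data for both are collected outside the trial.

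- **Intervention cost.** "Intervention costs will be assessed using structured interviews with study nurses, doctors and other relevant personnel at 3-4 of the participating hospitals". On what the interviews must deliver: "The purpose of these interviews is to describe and quantify the resource use relating to the intervention (e.g. the number of telephone calls", with staff time and IT support as further examples. The same interviews cover resource use "relating to patient telephone contact in the control arm".
- **Derived hospital cost.** Procedures, admissions, ambulatory contacts and costs are taken for each participant from national registries.

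On timing, Data collection and analysis says: "Data on resource use and costs for the health economic evaluation will be collected as a retrospective study upon completion of the trial". It describes the intervention part as an expert assessment of time and material. The Timetable places the economic evaluation in 2022, with recruitment from September 2018, and names eight recruiting sites.

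The intervention runs through AmbuFlex. Under Implementation of the intervention, weekly answers are "transferred in real time to a computer server, where notifications are generated and sent to clinicians if the prespecified symptom thresholds are exceeded". The Study plan section says that a detrimental change leads to contact from a study nurse.

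For uncertainty, the Statistics section and sub-study 3 (Analysis) specify bias-corrected non-parametric bootstrap intervals. Sub-study 3 adds sensitivity analyses without naming their parameters. Neither says how interview values are assigned to patients or whether they are resampled.

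**The concern.** Interviews are a normal source for how long a call takes and who makes it. They are a weak source for how many calls each patient generated over several years, and here volume is explicitly one of the things they must quantify. The trial's own system produces, for each patient, the event that starts most intervention contacts.

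Three features of this trial make a recalled average a poor substitute for a count:

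1. The protocol committee may adjust the threshold algorithm during the study (Defining the PRO application). Volume may change over time, and recall at the end may reflect the latest version.
2. Under the notification rules in the Appendix, a persisting symptom notifies only once unless it worsens further or has improved in between, whereas coughing blood notifies every time. Volume is therefore likely to be uneven across patients.
3. Patients leave the study at progression or stay for up to two years (Study period). Exposure to the intervention differs by patient, and a flat average would give short and long stays the same cost.

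At stake are the accuracy of one cost component and, through it, the cost difference and the incremental cost-effectiveness ratio. There is also a question of how uncertainty in that component reaches the reported intervals.

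**Working it through.** The documents state no cost, contact-volume or interval figure on this point, so there is nothing to reproduce. The check has two parts.

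**1. Sections side by side**

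| Quantity | Planned source | Held per patient by the trial? |
|---|---|---|
| Notifications, experimental arm | none planned for costing | yes: generated by the server from individual answers |
| Calls that follow a notification | interviews | not stated |
| Minutes and staff grade per call | interviews | not stated |
| Other telephone contact, either arm | interviews (named for the control arm) | not stated |
| Visits, admissions, scans | registries | per patient, outside the trial |

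The documents do not promise a retained notification log. The rules compare each answer with the latest week, and weight with baseline, so responses must be held over time. Data collection and analysis also says that trial data are stored in AmbuFlex and passed to REDCap. Counts for the structured items could therefore be rebuilt by applying the algorithm version in force at the time. The trial already plans to classify the CT scan at progression by whether a notification prompted it.

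**2. Possible size**

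Input from the documents: 246 patients per arm. Assumed, not in the documents:

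- eight sites of equal size, 3 or 4 of them interviewed;
- one mean intervention cost applied to all experimental patients;
- equal standard deviation (SD) of hospital cost in both arms;
- components independent, unless stated.

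*Intervention component alone*, 95% half-width as a share of its mean:

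- Site sampling: 1.96 × CV × √[(1/k)(1 − k/8)]. For a between-site coefficient of variation (CV) of 0.2, this is 18% with k = 3 and 14% with k = 4. For CV 0.5 it is 45% and 35%.
- Patient variation: 1.96 × CV/√246. For CV 0.5, 1.0 and 1.5, this is 6%, 12.5% and 19%.

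*Total cost difference.* Let m be mean intervention cost divided by the SD of hospital cost. In units of that SD, the standard error (SE) from hospital cost alone is √(2/246) = 0.0902, and the 95% half-width is 1.96 × 0.0902 = 0.177.

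- A proportional recall error b shifts the difference by b × m/0.177 half-widths. For example, 0.5 × 0.20/0.177 = 0.57.
- Adding site and patient variation (k at its midpoint, 3.5; CVs as above) multiplies the SE by √[1 + (V_patient + V_site)/(2/246)], where V_patient = (CV_patient × m)²/246 and V_site = (CV_site × m)²(1/3.5)(1 − 3.5/8).

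| m | Shift from 20% error | Shift from 50% error | Rise in SE |
|---|---|---|---|
| 0.01 | 1% | 3% | under 0.1% |
| 0.05 | 6% | 14% | 0.1-0.8% |
| 0.10 | 11% | 28% | 0.5-3% |
| 0.20 | 23% | 57% | 2-11% |

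Shifts are shares of the 95% half-width.

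Independence may be optimistic, because notifications can lead to visits and scans. With patient variation only (CV 1) and a correlation r of 0.3-0.6 with hospital cost, the SE multiplier is √[(2 + m² + 2rm)/2]. The rise is 0.8-1.6% at m = 0.05, 1.7-3.2% at 0.10 and 4-7% at 0.20.

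Throughout, bias from a wrong volume matters more than missing variance.

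**The case against.** The strongest defence is that expert assessment is a declared costing choice, for one component of a secondary endpoint evaluated after the trial, and that a server log would not replace it. A notification is not a call. The documents do not say that the system records calls made, repeat attempts or duration. Patients are also told to telephone the department themselves, and such calls create no notification. A missed questionnaire leads to a text reminder and an entry on the staff list, not to a required call. Notification counts could therefore overstate or understate telephone workload. All of this stands, so the interviews cannot be dropped.

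A second objection is that logging one arm and interviewing about the other would compare two measurement methods. It is met by limiting the log to contacts triggered by a notification, which exist only in the experimental arm, and using one interview method for all other telephone contact in both arms.

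A reader might also infer stronger claims that the documents do not support:

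- *That contact volume drives the cost endpoint, or that the whole cost difference rests on recall.* No cost sizes are given, and hospital costs come per patient from registries. The intervention can also change visits and scans, which fall in that registry component.
- *That the bootstrap interval leaves this variation out.* That would follow if one mean were applied to everyone and only patients were resampled. The plan does not say so, and the unspecified sensitivity analyses might cover it.
- *That sites in this trial are known to differ in workload.* The Feasibility section says "This project also demonstrated large differences between hospitals, which could be due to differences in regional health-it resources", but about a 2013-2015 data-collection project, not about calls in this trial.
- *That a number of miscounted contacts can be stated.* Trigger rates are not given, and counting 52 forms per patient-year ignores exits at progression and deaths.

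**Conclusion.** The point holds for the intervention-cost component. Its volume, including the number of calls, is to be quantified by retrospective interviews at 3-4 hospitals, while a closer per-patient measure of the triggering events exists in the trial's own system and is not planned for use. This is a choice of a weaker data source, not merely a missing detail.

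Its effect on the total cost difference is not determined by the documents. Under the assumptions above it is small if mean intervention cost is 1-5% of the SD of hospital cost: a shift of at most 14% of the 95% half-width and, with independent components, an SE rise below 1%. At 10-20% the shift is 11-57% of the half-width and the SE rise about 0.5-11%. The recall errors, CVs, equal site sizes and cost ratios are all assumed.

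The overall survival analysis and the registry-based hospital costs are unaffected.

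**What to change.** Revise the Data and Analysis parts of sub-study 3 as follows:

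1. Take the number of notifications per experimental-arm patient from AmbuFlex, at all sites, from randomisation to study exit. Keep the dates, so that counts can be cut at the one-year horizon and linked to the algorithm version in force.
2. Use the interviews for minutes and staff grade per contact, for the share of notifications that led to a call and, by the same method in both arms, for all other telephone contact.
3. Multiply volume by unit time and wage to give a patient-level intervention cost, and enter it with the registry cost in the bootstrap.
4. Name minutes per contact and calls per notification as parameters to be varied in the planned sensitivity analyses.

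The cost is one data extract and a rewritten paragraph. The remaining weakness is that notifications are an imperfect proxy for calls and may err in either direction, which is why step 4 is needed.
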